After informed consent has been obtained, participants will be asked for the contact information (email address and phone number) so that the study team can stay in contact. Final enrollment of a participant will depend on identity verification. Since data collection for this study will take place remotely, participants will be required to submit a picture of an official ID document for verification of their identity and age, a procedure that [name] has found to be feasible in his previous studies. After verification of identity, participants will be enrolled into the study. Only the participant picture on the ID (headshot) will be retained for biochemical verification of smoking abstinence. The ID document will subsequently be deleted after validation of participant details for enrollment.

Baseline survey: Initially, all participants will complete a baseline survey on the online survey platform Qualtrics, to assess basic demographics, smoking and other tobacco use behavior, including e-cigarettes, nicotine dependence, quitting history and current quit motivation, frequency and intensity of smoking urges, and other substance use behavior including alcohol, cannabis, and other illicit drugs. Smoking-specific experiential avoidance, a measure to assess a person's willingness to experience negative mental states (e.g., urges, mood, thoughts), will be assessed with the Avoidance and Inflexibility Scale. Trait mindfulness will be assessed with the FIT-60 (Flexibility Index Test).¹⁴³ Baseline measures will also include trait negative affect and psychological distress.

EMA data collection: Before EMA data collections, participants will be contacted on the phone to receive detailed instructions on how to use the EMA study app. Participants will use their own smartphones and the study app to collect data on smoking situations over the course of 14 days (EMAs of smoking situations and smartphone location sensor data). Participants will complete 3 randomly prompted EMA surveys per day and will report every time they smoke a cigarette. A random subset of these cigarette reports will trigger up to 3 EMA smoking survey prompts per day.

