EMA momentary surveys: Smoking urges will be recorded with a single item in accordance with recommendations from the Society for Research on Nicotine and Tobacco. Additional questions will examine internal and external aspects of the situation. The number of questions asked will be limited to ensure they do not interfere with participants' daily activities. In addition, the EMA software will log participants geolocation based on GPS. All data will be time and date-stamped to allow time-specific analyses and determine high-risk periods for smoking.

EMA daily diaries: Thorough daily diaries will be collected to assess overall cigarettes, other tobacco product (including e-cigarettes), alcohol, cannabis, and other substance use (illegal drugs). Questions will also assess same occasion co-use of tobacco, alcohol, cannabis, and drugs (when participants were feeling under the influence of other substance).

Purpose of the EMA training phase: The EMA training phase serves multiple purposes: First, it allows participants to get used to the study app that will also deliver the intervention messages, and second, the collected data will allow us to generate an individual risk profile with regard to time of day and location (by combining timestamps, GPS data, and self-reported data) with the highest likelihood of smoking for each participant. We will use geofencing to generate geospatial buffers around these high-risk locations. In combination with time of day information to target high-risk time periods for smoking, these geofences will trigger delivery of intervention messages when a mobile device enters the area: A message can be triggered when a participant approaches a smoking location during one of the high-risk time windows. We will use our established protocol for triggering intervention messages that we have successfully used in a pilot trial.

Intervention phase - Micro-randomized trial with N=80 participants to determine message efficacy

The micro-randomized trial will determine if CBT and Mindfulness/ACT messages are superior to control messages in reducing the primary outcome momentary smoking urges. Based on participants' training

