A total of N=80 participants will be randomized into an EMA-only control group, parallel to the micro-randomized trial intervention group (Figure: Study overview). This group will conduct 14-day EMA only training phase just like the micro-randomized trial group, but will not be switched over to the intervention phase after these initial 14 days. Instead, participants will continue the EMA-only data collection procedure for an additional 30-days (analogous to the 30-day intervention phase of the micro-randomized trial). During these 30 days, the EMA-only control group will continue to receive 3 randomly prompted EMA surveys per day and an additional 3 EMA surveys triggered by smoking reports. By comparing this control group to the micro-randomized trial intervention group, we will investigate if intervention message delivery results in changes in smoking behavior over time (see analytical strategy Aim 2).

Follow-up assessments

Follow-up assessment in both groups will be conducted at end of treatment (45 days), 3-months, and 6-months post-randomization. Surveys will be delivered online via Qualtrics and will assess current behavior (number of cigarettes/day, self-reported 7-day point prevalence abstinence), quit attempts, current quit motivation, frequency and intensity of smoking urges, and other substance use behavior including alcohol, cannabis, and other illicit drugs. Surveys will also assess baseline ACT measures: Avoidance and Inflexibility Scale and the FIT-60 (Flexibility Index Test).

Saliva cotinine will be used to **biochemically validate 7-day point prevalence abstinence** at each follow-up. Participants self-reporting smoking abstinence at any follow-up point will be mailed a saliva test-kit

(NicAlert test strip) and instructed to send one picture each of providing the saliva sample and the test kit result. We will only receive pictures of the test process and result and not receive an actual saliva sample. The picture of the test process (participant providing the saliva sample) will be used to confirm that the participant provided the sample him- or herself.

2. Describe the number and type of study visits and/or contacts between the study team and the participant, how long they will last, and where/how they will take place.

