Moreover, we will explore aspects of intervention message-situation fit. We will test if specific locations (e.g., home, work, bars) impact intervention message efficacy. Mixed models will be estimated containing the predictors intervention type (CBT, Mindfulness/ACT, control), location (home, work, bar, other locations), and their interaction. We will explore other situational characteristics and intervention message-situation fit based on affect, arousal, stress, and the presence of other smokers. We do not have specific hypotheses about moderation effects of location and other situational characteristics, but findings will inform future interventions using adaptive messages over time to improve intervention-message situation fit and intervention efficacy.

5. Answer the following if they are relevant to your study design:

- A. If the study has different arms, explain the process for assigning participants (intervention/control, case/control), including the sequence and timing of the assignment.

We will use stratified block randomization to assign participants into the micro-randomized trial intervention group (N=80) and EMA-only control group (N=80). The stratification variable known to robustly impact smoking cessation success will be level of nicotine dependence (smoking within first 30 mins after waking, y/n).¹³¹ Gender will be used as additional stratification variable. We will generate a randomization table and participants will be assigned after baseline completion.

- B. If human biospecimens (blood, urine, saliva, etc.) will be collected, provide details about who will collect the specimen, the volume (ml) and frequency of collection, how the specimen will be used, stored, identified, and disposed of when the study is over. If specimens will be collected for use in future research (beyond this study), complete the “Biospecimen Repository” section below.

N/A

- C. If genetic/genomic analyses are planned, address whether the data will be contributed to a GWAS or other large dataset. Address returning unanticipated incidental genetic findings to study participants.

N/A

- D. If clinical or laboratory work will be performed at JHU/JHH, provide the JH Biosafety Registration Number.

N/A

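### Randomisation comes before a 14-day training phase that is identical in both arms, so people who leave before any message can be sent remain in the Aim 2 comparison

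*Combined protocol and SAP*

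**What the plan says.** - **Timing of assignment.** Section V.C.5.A describes stratified block randomisation by nicotine dependence and gender, and adds that "participants will be assigned after baseline completion". The only baseline the plan defines is the online survey in Section V.C.1: "Initially, all participants will complete a baseline survey on the online survey platform Qualtrics, to assess basic demographics, smoking and other tobacco use behavior". It precedes EMA data collection.
- **Training phase.** Of the control group, Section V.C.1 (Built-in parallel-group RCT) says: "This group will conduct 14-day EMA only training phase just like the micro-randomized trial group". It continues: "but will not be switched over to the intervention phase after these initial 14 days". The arms differ only from that point.
- **Role of the training data.** Section V.C.1 (Purpose of the EMA training phase) says that "the collected data will allow us to generate an individual risk profile". The geofences and time windows that trigger messages come from that profile.
- **Follow-up.** Surveys are "conducted at end of treatment (45 days), 3-months, and 6-months post-randomization".
- **Analysis.** Section III.B (Aim 2) has missing data multiply imputed and the full sample analysed. The Aim 2 GEE in Section V.C.4 includes group, gender, nicotine dependence and whatever differs by group at baseline. Cigarettes/day before assignment is not a fixed covariate.
- **Blinding.** Section V.C.5.F.a says that study staff are not blind. The plan does not say when participants learn their arm.

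**The concern.** For 14 days after randomisation nothing distinguishes the arms except knowledge of the allocation. Loss in this window adds people to the intervention arm who largely cannot receive what that arm is meant to test, and the plan neither states an expected loss nor says how such people are handled.

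The consequence depends on their follow-up. If they answer the later surveys and are analysed as observed, they contribute no message effect and the contrast in cigarettes/day is diluted. If they are missing and imputed from a model with arm but no exposure term, people who never had a message receive values typical of those who did. The contrast is then not diluted, but it estimates the effect as if nobody had left, and precision is lost.

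There is also an opening for bias. Unblinded staff make the app-training call and the compliance check-ins (Sections V.C.1 and V.C.2). If allocation is known to them or to participants during training, retention or smoking could differ by arm before any message is sent.

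**Working it through.** **Order of events.** Baseline survey, assignment, 14 days of EMA in both arms, then 30 days of messages or continued EMA. 14 + 30 = 44 days, which fits an end-of-treatment survey at day 45 after randomisation. The study overview figure is not shown, but the text is consistent.

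**Inputs from Section III.B (Aim 2).** 80 per arm, alpha 0.05 (two-sided assumed), d = 0.651 (f = 0.326), stated power 0.80. The raw difference behind d is 3.8 + 0.8 = 4.6 cigarettes/day. The training loss q is not in the documents; 10%, 15% and 20% in each arm are assumptions.

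**The plan's own figure.** For a two-sample t test the noncentrality is λ = d√(n/2) with 2n − 2 degrees of freedom. With n = 80, λ = 0.651 × √40 = 4.117 and power is 0.984, not 0.80; power 0.80 needs 39 per arm. Repeated-measures ANOVA with 2 to 4 measures and correlations of 0 to 0.8 gives 0.946 or more at N = 160. The stated power is thus conservative for its own effect size. That is a separate matter and does not support this point. The effect that 80 per arm does detect with power 0.80 in one comparison is d = 0.446.

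**Assignment before training, leavers followed with no effect.** The effect becomes d(1 − q) at n = 80, so λ = d(1 − q)√40. For d = 0.651 and q = 0.10: 0.651 × 0.90 × 6.325 = 3.706. The raw difference falls from 4.6 to 4.14, 3.91 and 3.68 cigarettes/day at 10%, 15% and 20%.

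**Assignment at day 14, same enrolment.** The effect stays d and n becomes 80(1 − q), so λ = d√(40(1 − q)). For d = 0.651 and q = 0.10: 0.651 × √36 = 3.906.

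| Assumed q | n per arm if late | d=0.651: early, diluted | d=0.651: late | d=0.446: early, diluted | d=0.446: late |
|---|---|---|---|---|---|
| 10% | 72 | 0.958 | 0.973 | 0.713 | 0.757 |
| 15% | 68 | 0.936 | 0.965 | 0.664 | 0.733 |
| 20% | 64 | 0.906 | 0.955 | 0.611 | 0.707 |

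Under this model late assignment always does better, because √(1 − q) exceeds 1 − q: dilution multiplies the required N by 1/(1 − q)², loss of numbers only by 1/(1 − q). At d = 0.651, diluted power reaches 0.80 when 0.651(1 − q) = 0.446, that is q = 1 − 0.446/0.651 = 0.315, about 32%.

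**Assignment before training, leavers missing and imputed by arm.** If they carry no information, the effective size is roughly n(1 − q) at an undiluted d, so power is close to the late columns. Here late assignment gains a clear estimand rather than power.

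**Numbers randomised.** From 160 enrolled: 160 × 0.90 = 144, 160 × 0.85 = 136, 160 × 0.80 = 128. To randomise 160 at 10%, 15% or 20% loss, enrol 160/(1 − q) = 178, 189 or 200.

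**The case against.** Randomising before a run-in is a legitimate choice: it keeps everyone enrolled in the comparison, while assignment at day 14 narrows the population to people who complete training. That stands, and it is the price of the change. At the plan's own effect size the gain is also small: 1.5, 2.9 and 4.9 percentage points at 10%, 15% and 20%.

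The plan has retention measures: compliance check-ins, $2 per EMA day, and $90 for completing at least 75% of prompts. It sets no minimum amount of training data, so partial data might still yield a risk profile. Leavers are therefore largely, not certainly, beyond the reach of messages.

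Four stronger readings are tempting and not supported.
- A reader might infer that the effect is necessarily shrunk. It is shrunk only if leavers are followed and analysed as observed.
- A reader might infer that the training data are being misused, or are lost, as a baseline. The plan never proposes them as the Aim 2 baseline, and the survey measures smoking before assignment. All that is lost is a pre-randomisation diary covariate.
- A reader might infer that arm-dependent dropout is established. The documents leave it open, since the time at which participants learn their arm is not stated.
- A reader might infer that the 45-day survey will fall inside the intervention phase if onboarding is slow. The 45 days may simply label the day after 44 days of EMA; this is mostly a matter of wording.

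**Conclusion.** The point holds as a worthwhile and inexpensive design improvement, not as an error that undermines Aim 2. The text supports assignment before an identical 14-day phase, with no stated allowance for loss in that phase and no rule for those lost.

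Its size depends on two things the documents do not give: the training loss and how leavers are followed. Under dilution, power at d=0.651 stays above 0.80 until about 32% are lost. The cost becomes material for effects nearer the detection limit, where a 20% loss leaves 0.611 against 0.707 with late assignment. Taking 0.611 as the expected power would go too far, because d=0.446 is solved from the sample size and is not the plan's assumption. The figures also rest on a single two-sample t comparison, equal loss in both arms and no effect in leavers; the planned GEE uses three follow-ups.

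The case for preventing arm-dependent behaviour before treatment, and for a defined estimand, does not depend on these power figures.

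**What to change.** 1. Keep the strata and the randomisation table, but assign at the end of day 14, when the app is switched over.
2. Count follow-up from that assignment, and reword the follow-up times to match.
3. Include cigarettes/day before assignment as a fixed covariate in the Aim 2 GEE: the mean of the day 1 to 14 diaries, or the baseline survey value. The diary mean has the merit of following any change due to self-monitoring, which Section V.C.5.F.c expects may occur. The gain in precision cannot be stated, as the documents give no correlation.

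Cost: an amendment to the timing of randomisation, the follow-up clock and the consent wording. Fewer than 160 are randomised from 160 enrolled (144 to 128 at 10% to 20% loss) unless enrolment rises to about 178 to 200. Inference is to people who complete training.

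If early assignment is kept, conceal the allocation from participants and contact staff until day 14, and adjust for cigarettes/day from the baseline survey. Also state an assumed training loss, the estimand, and how people who leave before the intervention are followed and imputed.
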